### *CM analysis*

We will use Concept Systems software to conduct the analytical steps to identify and create visual representations of emergent themes and empirically assess whether key demographic characteristics such as gender, region, age group, insurance/coverage type, etc., are associated with systematic thematic variations. First, we will construct a similarity matrix that identifies how often statements are grouped together across all participants [57, 85]. Next, we will apply multidimensional scaling techniques to calculate the two-dimensional “distance” between each statement. This will result in a two-dimensional visual representation of the location of each statement relative to other statements. The final step will involve hierarchical cluster analysis to group similarly located statements within a specific participant category. As a participatory study, this step will be accomplished collaboratively by including review and feedback from the Advisory Board and AIE Consultants. Final concept maps and labels will be presented to the Advisory Board for approval, and then used to empirically assess (via t-tests) the extent to which demographic characteristics influence the rankings of each concept cluster (e.g., importance or feasibility of addressing specific issues).

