**Improving Native American Elder Access to and Use of Healthcare**  
**NCT03550404**  
**February 7, 2023**

## Background

Although health care is a legal right of members of federally recognized Tribes, American Indians (AIs) still have persistent disparities in health status and access to services. They suffer from higher rates of illness, substance use problems, and mental distress compared to other populations in the United States (U.S.). At the same time, AIs are significantly less likely to have health insurance coverage and often live in rural areas or on reservations, where access to health care is more difficult. These disparities especially affect American Indian elders (AIEs), while few data exist on the health, insurance status, and access to health care of AIEs specifically. This study employs a participatory and mixed-method research design to understand AIEs' experiences with health care and health insurance in order to improve healthcare practices and policies for this population, which is largely excluded from national and state discussions of health reform.

Compared to non-Hispanic whites, AIs report poorer physical and mental health and are less likely to see a medical doctor or have a usual source of health care [1]. Adults who are AI suffer from disproportionately high incidences of cerebral vascular disease, diabetes mellitus, heart disease, hypertension, obesity, and stroke [1–10], and are more likely to have substance use problems and mental distress [11–15]. Almost one-fourth of AIs have a disability [16]. With more than 1.2 million, or nearly a quarter, of AIs without healthcare coverage in 2011, lack of insurance is implicated in these disparities [14]. Historically, this has been especially true for AIEs, as many as one in four of whom were uninsured a decade ago [17], with estimates of their current insurance rates varying [18]. Moreover, young AIEs, 55–64 years old, are more likely to be uninsured compared to all other adults in the same age bracket [14, 19]. These uninsured AIEs are more likely to go without health care compared with insured AIEs, especially on reservations, where AIEs are more likely to report lack of health insurance compared to those in urban areas [19]. Geographic areas with high concentrations of AIs also have significant disparities in access to and use of health services, and particularly preventive care, such as cancer screening [20].

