**Table 1. Overview of study phases, methods, and timeline**

	Phase 1: Convening AIE Advisory Board and Training AIE Consultants	Phase 2: Semi- structured Interviews and CM with AIEs (Aims 1 and 2)	Phase 3: Semi- structured Interviews and CM with Key Stakeholders (Aim 3)	Phase 4: Development, Implementation, and Evaluation of AIEONG (Aim 4)
Participant Category	
 
AIE leaders and Allies (<math>n = 20</math>; 8 Advisory Board members and 12 AIE Consultants)
 
	
 
AIEs (<math>n = 96-144</math>; 24-36 per region)
 
Sample stratified by age and gender to ensure adequate representation for men and women aged 55-64 and 65+
 
	
 
Outreach workers (<math>n = 12</math>)
 
Healthcare staff/providers (<math>n = 12</math>)
 
Public-sector administrators (<math>n = 12</math>)
 
Tribal leaders (<math>n = 12</math>)
 
	
 
AIE Navigators (<math>n = 16</math>; 8 in P1 and 8 in P2)
 
AIEs (<math>n = 48</math>; 12 per region)
 
Healthcare staff/providers (<math>n = 48</math>; 12 per region)
 

Sampling and Recruitment Strategy	
 
Reputational case selection (candidates identified based on recommendations from members of research team and local experts from NMICoA) [86]
 
	
 
Stratified purposive sample (candidates selected from AIE senior centers, healthcare settings, AIE Consultant referrals, and advertising to capture variations in the target population) [67]
 
	
 
Reputational case selection (candidates identified based on recommendations from local experts from NMICoA, healthcare support groups, and tribal programs) [86]
 
	
AIE Navigators:
 
 
Reputational case selection (candidates identified based on recommendations from local experts and interest in implementing AIEONG) [86]
 

				
AIEs and healthcare staff/providers
 
 
• List sampling (candidates selected from master lists that will be compiled from attendance records of individuals who participate in AIEONG-related activities or have contact with an AIE Navigator)
 

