#### *Phase 2: Semi-structured interviews and concept mapping (aims 1 and 2) with AIEs*

##### *Participants and recruitment*

To achieve Aims 1 and 2, we will use multiple strategies to recruit a total of 96 AIEs for completion of semi-structured interviews. We will identify potential participants by regularly visiting AI senior centers in the four regions (North, South, West, and Albuquerque), plus veterans organizations, community health fairs, and quarterly NMICoA meetings. We will use a qualitative sampling strategy designed to represent the range of views within a group (or region) to determine similarities and differences in knowledge, beliefs, and experiences related to the issues investigated [66, 67]. The domains of interest here are insurance coverage, help-seeking and healthcare experiences, and factors affecting AIE access and utilization. We will use purposive sampling to recruit candidates able to discuss the elements of these domains. Unlike probability sampling procedures, in purposive sampling there is no way to precisely estimate how many of each type of participant might be required for a study. However, qualitative researchers generally agree that in-depth interviewing requires between 12 and 26 persons within a designated group [67– 69]. We have calculated the interview sample sizes with AIEs accordingly; each is large enough to examine a range of experiences related to the topics at hand. If, during the process of obtaining informed consent from AIE participants, the researcher or AIE Consultant feels that a potential participant may not be able to understand or complete study procedures, they will

administer the MINI-COG [70] to test for cognitive impairment. Participants deemed positive for cognitive impairment will not be eligible to participate.

After completion of the semi-structured interviews, we will use the same strategies to recruit 48 AIEs who can read in English to participate in the remaining CM exercises (described below). These may, but will not necessarily, include individuals who participated in semi-structured interviews.

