#### *CM data*

The remaining CM exercises of pile-sorting and ranking will take place at a later date to reduce the possibility of participant fatigue, and last between 45 and 60 min [78–80]. The CM method is becoming increasingly prominent in community-driven, participatory research that seeks to determine locally relevant intervention strategies [81, 82]. It is useful when working with diverse stakeholders who may hold different perspectives on insurance and healthcare services. Two important CM goals are to further explore issues and themes identified in the qualitative interviews and to then generate a list of action items that are truly relevant to improving access and utilization among AIEs. The research team will identify approximately 80 unique statements from AIE answers to the focal questions contained in the semi-structured interview (i.e., “What factors make it easy or hard for American

Indian elders to get good health care?” “What factors make it easy or hard for American Indian elders to get good health insurance?”) and inscribe each statement on a card (e.g., “Having to travel long distances to get to the clinic,” “Having to wait too long for an appointment”). During the CM exercise, the participants will be asked to put similar

statements into piles. After the participant has created piles by grouping the statements, the researcher will ask the participant to describe the reasons for these choices and label each pile with a theme (e.g., “Transportation”). Finally, each participant will be asked to rank or rate each statement using a 1-to 10-point scale on three dimensions: 1) how much each statement affects American Indian elders; 2) how common each statement is among American Indian elders; and 3) how easy each statement would it be to change. This may appear a daunting task, but participants often see it as fun and engaging. Members of our research team have successfully deployed this technique with other vulnerable populations, including persons with serious mental illnesses.

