### *Data analysis*

#### *Quantitative analysis*

We will use the quantitative data to summarize and compare characteristics of the AIE participants. Where possible, we will conduct descriptive comparisons that assess for differences between our study and AI and non-AI samples from other external studies that use the same questions. These results will help evaluate the extent to which the AIEs in our sample experience health access and utilization-related disparities. The anticipated quantitative analytical techniques include chi-square tests, t-tests, and ANOVAs. We will use multivariate regression strategies in exploratory analyses to identify characteristics associated with insurance and healthcare access and utilization outcomes among AIEs. An estimate of power is inappropriate given the qualitative sampling strategy guiding our overall sample selection.

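### Concept-mapping cluster ratings are compared by coverage type with one-at-a-time t-tests, so if coverage and ratings both vary by age band, part of an age difference may be reported as a coverage difference

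*Combined protocol and SAP*

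**What the plan says.** The CM analysis section for Phase 2 sets out to "empirically assess whether key demographic characteristics such as gender, region, age group, insurance/coverage type, etc., are associated with systematic thematic variations". Age group and coverage type therefore stand side by side as grouping variables. Once the Advisory Board has approved the maps, they are to be "used to empirically assess (via t-tests) the extent to which demographic characteristics influence the rankings of each concept cluster". The t-test is the only test named for the ratings, and the section mentions no covariate, stratification or within-age comparison.

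The ratings come from participants who "rank or rate each statement using a 1-to 10-point scale on three dimensions". For this exercise, "we will use the same strategies to recruit 48 AIEs who can read in English to participate in the remaining CM exercises". These people may or may not have been interviewed earlier.

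Table 1 describes the Phase 2 participants, 96 to 144 elders, with the note "Sample stratified by age and gender to ensure adequate representation for men and women aged 55-64 and 65" and over. It gives no quota per stratum and does not say how the 48 CM elders divide by age.

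The only multivariable modelling is in the Quantitative analysis section: "We will use multivariate regression strategies in exploratory analyses to identify characteristics associated with insurance and healthcare access and utilization outcomes among AIEs". CM ratings are not among those outcomes.

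**The concern.** A t-test on coverage type compares the ratings of two coverage groups whatever else differs between them. If one group is older on average, and older elders rate barriers differently, the coverage contrast carries part of the age contrast. A separate t-test on age group would show a difference too, but the two tests together cannot say which characteristic accounts for it.

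The overlap is plausible here. The Phase 2 sample is stratified at 65, and Medicare is among the programs that the interviews ask about. That Medicare coverage is more common from 65 on is taken as an assumption, because the documents do not give it.

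The point matters because the ratings are used. According to Phase 4, CM findings show what stakeholders would put first and regard as changeable, and the barriers presented in the navigation guide are those ranked through CM. Coverage is also the subject of Aim 1, so a difference labelled as a coverage difference is likely to be taken up by readers.

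**Working it through.** **Inputs from the documents:** 48 CM elders; age bands 55-64 and 65 or over; ratings from 1 to 10; t-tests for cluster ratings. The plan gives no effect size, standard deviation (SD), significance level or power for this comparison, so there is no figure of its own to reproduce.

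**Inputs assumed:** 24 elders per band; a two-group Medicare/non-Medicare contrast; Medicare coverage by band over a range; two-sided 5% tests.

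**Step 1. Share of an age difference that reaches the coverage contrast.** If age and coverage effects add, the expected unadjusted difference equals the coverage effect plus the age effect times

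pass-through = P(65+ | Medicare) − P(65+ | non-Medicare).

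| Medicare at 65+ / 55-64 | P(65+ given Medicare) | P(65+ given non-Medicare) | Pass-through |
|---|---|---|---|
| 95% / 15% | 22.8 / (22.8 + 3.6) = 0.86 | 1.2 / (1.2 + 20.4) = 0.06 | 0.81 |
| 95% / 30% | 22.8 / (22.8 + 7.2) = 0.76 | 1.2 / (1.2 + 16.8) = 0.07 | 0.69 |
| 80% / 40% | 19.2 / (19.2 + 9.6) = 0.67 | 4.8 / (4.8 + 14.4) = 0.25 | 0.42 |
| 60% / 40% | 14.4 / (14.4 + 9.6) = 0.60 | 9.6 / (9.6 + 14.4) = 0.40 | 0.20 |

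If the bands differed by one point on the 10-point scale, for illustration, and coverage had no effect of its own, the coverage contrast would show 0.42 to 0.81 points in the first three rows and 0.20 in the last.

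**Step 2. Effect on the test.** A simulation (5,000 runs per case, 48 elders, ratings with SD 1) set the coverage effect given age to zero and the age effect to 0.5 or 0.8 SD. It compared the t-test with a linear model of coverage plus age band. Rates are among runs in which the adjusted model could be fitted.

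| Coverage at 65+ / 55-64 | t-test rejects (0.5; 0.8 SD) | Mean spurious difference, SD | Adjusted model rejects | Adjusted SE, SD |
|---|---|---|---|---|
| 50% / 50% | 4.5%; 5.2% | about 0 | 4.9%; 5.1% | 0.29 |
| 60% / 40% | 6.5%; 7.6% | 0.10; 0.16 | 5.4%; 4.2% | 0.30 |
| 75% / 25% | 12.8%; 25.6% | 0.25; 0.41 | 4.6%; 5.6% | 0.34 |
| 90% / 10% | 27.3%; 56.5% | 0.40; 0.64 | 5.2%; 5.1% | 0.52 |
| 95% / 5% | 33.3%; 66.5% | 0.45; 0.72 | 4.8%; 5.7% | 0.71 |

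The spurious differences agree with Step 1: at 60%/40%, 0.20 × 0.5 = 0.10 and 0.20 × 0.8 = 0.16. With no age effect, the t-test rejected in 4.5% to 5.4% of runs at every level of alignment. Both conditions are therefore needed: coverage must differ by band, and ratings must differ by band.

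**Step 3. Cost of adjusting.** The unadjusted standard error is about 0.30 SD, an interval of roughly ±2 × 0.30 = 0.60 SD. Adjusted, it is about ±1.04 SD at 90%/10% (2 × 0.52) and ±1.42 SD at 95%/5% (2 × 0.71). At 95%/5% the model could not be fitted in about 8% of runs, which matches the chance that all 48 elders align perfectly, 0.95^48 = 0.085.

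**The case against.** The strongest reply is that this is a primarily descriptive study led by its qualitative component, and that an unadjusted difference by coverage is a valid description. The CM section itself first speaks of association. Age group is compared too, so an age pattern would be visible, and the interview findings are examined by age and by coverage. All of this stands, and it limits the consequence to a misread descriptive contrast. It does not supply an analysis that separates the two characteristics for the ratings, and the sentence that names the t-tests speaks of influence.

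A second reply is that Medicare/non-Medicare is not the plan's contrast. The documents also discuss Medicaid, Exchange plans and managed care, and such groupings need not divide at 65. This is right, and the percentages hold only for the assumed contrast.

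A reader might infer more: that coverage is known to follow the age split, so that age differences will be reported as insurance differences. The documents do not support this. The nearest statement in the Background, that "young AIEs, 55–64 years old, are more likely to be uninsured compared to all other adults in the same age bracket", compares elders aged 55-64 with other adults of that age, not with elders aged 65 or over. Nothing says that ratings vary with age, and the stratification is stated for the Phase 2 sample as a whole and only implied for the 48.

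A reader might also infer that the guide's content would be targeted by coverage type in error. No such targeting is planned: the logic model is organised by socio-ecological level, and the Advisory Board approves the guide.

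Finally, adjustment helps least where alignment is strongest. At 95%/15% only 1.2 elders aged 65 or over would be expected to lack Medicare. That is a reason to report that the effects cannot be separated, and no reason to present the unadjusted contrast alone.

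**Conclusion.** The concern holds in conditional form. The plan tests coverage type and age group separately by t-test and states no analysis that tells them apart for CM cluster ratings. Misattribution is possible but not certain. Its size for a Medicare/non-Medicare contrast is about 42% to 81% of any age difference, under assumed coverage of 80%/40% to 95%/15% and 24 elders per band. It is small if coverage is only weakly linked to age, and nil if ratings do not differ by age. This is an inexpensive improvement to a descriptive analysis and does not threaten the study's main purpose. The Quantitative analysis section needs no change, since exploratory regression is already planned there.

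**What to change.** In the CM analysis section, for comparisons of cluster ratings by coverage type:

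1. Cross-tabulate coverage type by age band (55-64, 65 or over) for the CM participants.
2. Beside the unadjusted difference, report the coverage contrast from a linear model of the cluster rating on coverage type and age band, or the contrast within each band, with a confidence interval.
3. Where a band holds almost no elders in one coverage group, state that age and coverage cannot be separated.
4. Replace the wording about influence with wording about association, as in that section's opening sentence.

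The cost is a few lines of text and one table. Both variables are already grouping variables in the plan, but they must be on record for CM elders who were not interviewed. The statistical price is precision: with 48 elders the adjusted interval will be wider, and under strong alignment the contrast may not be estimable. That should be reported as a limit of the data.

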### Mixed-methods triangulation

The research team will integrate the quantitative, qualitative, and CM-derived findings to develop a more comprehensive understanding of the data [56, 58]. First, quantitative analyses of key participant characteristics will sharpen and guide deeper-level analyses of the qualitative data. Second, we will summarize the various analyses and then conduct a side-by-side comparison of findings from the three data sources to evaluate the degree of convergence related to our aims. Such comparisons will make it possible to link our data across sources; for example, how people enumerate their healthcare experiences (quantitative), how they describe their experiences in their own words (qualitative), and which experiences they would prioritize if given the opportunity to change (CM). Such comparisons will prompt more nuanced analyses when findings diverge, increase the validity and credibility of overall results, and foster a comprehensive understanding of AIE experiences with insurance and healthcare systems, and potential strategies for enhancing these experiences.

## *Phase 3: Semi-structured interviews and concept mapping with key stakeholders (aim 3)*

### *Participants and recruitment*

To achieve Aim 3, we will use reputational case selection to solicit local expert recommendations for persons who best exemplify OWs (n = 12), healthcare staff/providers (n = 12), public administrators (n = 12), and tribal leaders (n = 12) in championing, developing, implementing, or engaging in outreach, enrollment, and service delivery planning or provision to AIEs [86]. Local experts will include NMICoA Health Committee members and local partners with expertise in Native American health policy. We will create a final list of candidates and, based on Advisory Board advice, rank those to contact first via phone, email, and mail to participate.

### *Data collection*

#### *Quantitative data*

Participants will first complete a brief survey to capture demographic data and key quantifiable information regarding their work experience in public administration, health care and/or insurance, and involvement in ACA and other reforms.

#### *Qualitative data*

Participants will take part in a semi-structured interview specific to each participant category. The OWs and healthcare staff/providers will be asked about their work roles and responsibilities related to AIEs; organizational factors affecting their work with AIEs; the effect of the ACA and other key reforms on this work, insurance, and healthcare options for AIEs; the circumstances in which AIEs can act upon these options; and the health literacy challenges faced in communicating health-related information to AIEs. Interviews with public sector administrators and tribal leaders will center on state and tribal efforts to incorporate AIEs into public insurance programs, facilitate better access to affordable health care, increase health literacy at the level of patients and organization, and reduce AIE health disparities. We will inquire into the particular role that they and others play in these efforts and factors that help or hinder initiatives to address AIE needs in the changing healthcare environment. Interview guides for all stakeholders will include the same two focal questions with pertinent probes (i.e., “What factors make it easy or hard for American Indian elders to get good health care?” “What factors make it easy or hard for American Indian elders to get good health insurance?”) posed to AIEs as the first step of the CM process.

#### *CM data*

At a later date, we will invite these diverse participants to take part in the same CM activities discussed above for Phase 2 (i.e., sorting and ranking).

#### *Data analysis*

Data analysis for Phase 3 will follow the same procedures enumerated above for Phase 2, including qualitative, quantitative, CM analysis, and mixed-methods triangulation. Data analyses from Phase 3 will also be integrated into those generated during Phase 2 in order to evaluate the degree of convergence or divergence across stakeholder types (i.e., AIEs, OWs, healthcare staff/providers, public sector administrators, and tribal leaders), as well as to expand on, and provide nuance to, Phase 2 quantitative and qualitative findings.

